## **5. CONDUCT OF THE STUDY**

### **5.1. Regulatory and ethical considerations, including the informed consent process**

The study will be conducted in accordance with all applicable regulatory requirements.

The study will be conducted in accordance with the International Conference on Harmonisation (ICH) Guideline for Good Clinical Practice (GCP), all applicable subject privacy requirements and the guiding principles of the Declaration of Helsinki.

The study has been designed and will be conducted in accordance with the ICH Harmonised Tripartite Guideline for clinical investigation of medicinal products in the paediatric population (ICH E11) and all other applicable ethical guidelines.

GSK will obtain favourable opinion/approval to conduct the study from the appropriate regulatory agency, in accordance with applicable regulatory requirements, prior to a site initiating the study in that country.

Conduct of the study includes, but is not limited to, the following:

- Institutional Review Board (IRB)/Independent Ethics Committee (IEC) review and favourable opinion/approval of study protocol and any subsequent amendments.
- Subject's parent(s)/LAR(s) informed consent as appropriate.
- Investigator reporting requirements as stated in the protocol.

GSK will provide full details of the above procedures to the investigator, either verbally, in writing, or both.

Freely given and written or witnessed/thumb printed informed consent must be obtained from each subject's parent(s)/LAR(s) as appropriate, prior to participation in the study.

GSK Biologicals will prepare a model Informed Consent Form (ICF) which will embody the ICH GCP and GSK Biologicals required elements. While it is strongly recommended that this model ICF is to be followed as closely as possible, the informed consent requirements given in this document are not intended to pre-empt any local regulations which require additional information to be disclosed for informed consent to be legally effective. Clinical judgement, local regulations and requirements should guide the final structure and content of the local version of the ICF.

## **5.2. Subject identification and randomisation of treatment**

### **5.2.1. Subject identification**

Subject identification numbers will be assigned sequentially to the subjects whose parent(s)/LAR(s) have consented to their participation in the study, according to the range of subject identification numbers allocated to each study centre.

### **5.2.2. Randomisation of treatment**

#### **5.2.2.1. Randomisation of supplies**

The numbering of supplies will be performed at GSK Biologicals, using a block scheme randomisation in MATerial EXcellence (MATEX), a program developed for use in Statistical Analysis System (SAS®) (Cary, NC, USA) by GSK Biologicals. Entire blocks will be shipped to the study centres/warehouse(s).

To allow GSK Biologicals to take advantage of greater rates of recruitment than anticipated at individual centres in this multi-centre study and to thus reduce the overall study recruitment period, an over-randomisation of supplies will be prepared.

#### **5.2.2.2. Treatment allocation to the subject**

The treatment numbers will be allocated by dose.

##### **5.2.2.2.1. Study group and treatment number allocation**

The target will be to enrol 1600 eligible subjects who will be randomly assigned to four study groups in a 1: 1: 1: 1 ratio (approximately 400 subjects in each group).

Allocation of the subject to a study group at the investigator site will be performed using SBIR. The randomisation algorithm will use a minimisation procedure accounting for

centre and country. Minimisation factors will have equal weight in the minimisation algorithm.

After obtaining the signed and dated ICF from the subject's parent(s)/LAR(s) and having checked the eligibility of the subject, the site staff in charge of the vaccine administration will access SBIR. Upon providing the subject identification number, the randomisation system will determine the study group and will provide the treatment number to be used for the first dose.

The number of each administered treatment must be recorded in the eCRF on the Vaccine Administration screen.

When SBIR is not available, please refer to the SBIR user guide or the Study Procedures Manual (SPM) for specific instructions.

#### **5.2.2.2. Treatment number allocation for subsequent doses**

For each dose subsequent to the first dose, the study staff in charge of the vaccine administration will access SBIR, provide the subject identification number, and the system will provide a treatment number consistent with the allocated study group.

The number of each administered treatment must be recorded in the eCRF on the Vaccine Administration screen.

### **5.3. Method of blinding**

This study is observer-blind (double blind for the three lots of PCV-free HRV liquid vaccine and observer-blind for the liquid formulation versus the lyophilised formulation).

Data will be collected in an observer-blind manner. By observer-blind, it is meant that during the course of the study, the vaccines recipient and those responsible for the evaluation of any study endpoint (e.g., safety and reactogenicity) will all be unaware of which vaccine was administered. To do so, vaccine preparation and administration will be done by authorised medical personnel who will not participate in any of the study clinical evaluation assays.

The laboratory in charge of the laboratory testing will be blinded to the treatment, and codes will be used to link the subject and study (without any link to the treatment attributed to the subject) to each sample.

### **5.4. General study aspects**

Supplementary study conduct information not mandated to be present in this protocol is provided in the accompanying SPM. The SPM provides the investigator and the site personnel with administrative and detailed technical information that does not impact the safety of the subjects.

The burden of the study for the subject will be minimised as much as possible. For taking blood samples, three attempts at most should be performed. If the physician is not successful after the third attempt, he/she will make no further attempts. A local numbing cream or patch will also be offered at the discretion of the investigator prior to blood sampling, in order to minimise pain when blood samples are drawn.

### **5.5. Outline of study procedures**

The outline of study procedures is detailed in [Table 4](#).

**Table 4 List of study procedures**

Age	6-12 weeks	3-5 months	4-7 months	9-11 months
Epoch	Epoch 001			
Type of contact	Visit 1	Visit 2	Visit 3	Extended Safety Follow-up Contact
Time points	Day 0	Month 1-2	Month 2-4	Month 7-8
Sampling time points	Pre-Vacc		Post-Vacc 2	
Informed consent	•			
Check inclusion/exclusion criteria	•			
Check contraindications	•	•		
Check warnings and precautions	•	•		
Medical history	•			
Recording of gestational age	•			
Recording of demography	•			
History directed physical examination	•			
History of previous vaccination from birth	•			
Pre-vaccination body temperature	•	•		
Measure/record height and weight	•			
Randomisation	•			
Recording of Treatment number	•	•		
Blood sampling for anti-RV antibody determination (approximately 2 ml)	•		•	
Vaccination *	•	•		
Record regurgitation	•	•		
Distribution of diary cards	○	○		
Daily post-vaccination recording of solicited adverse events within 8 days (Day 0–Day 7) after each vaccination by subjects' parent(s)/LAR(s) in diary card.	•	•		
Recording of non-serious adverse events within 31 days (Day 0–Day 30) after each vaccination, by investigator	•	•	•	
Recording of GE episodes for all subjects	•	•	•	
Collection of stool samples if the child develops GE	•	•	•	
Return of diary cards		○	○	
Diary card transcription by investigator or designee		•	•	
Record any concomitant medication/vaccination in the diary card	•	•	•	
Record any intercurrent medical conditions	•	•	•	•
Recording of Serious Adverse Events (SAEs) and AEs leading to withdrawal	•	•	•	•
Phone Contact				•
Analysis on data collected up to Visit 3			○	
Study Conclusion				•

Note: The double-line border indicates the analyses which will be performed on all data obtained up to that visit or contact.

• is used to indicate a study procedure that requires documentation in the individual eCRF.

○ is used to indicate a study procedure that does not require documentation in the individual eCRF.

\* Two oral doses of the study vaccines will be administered at an approximate 1-month or 2-months interval to subjects, according to the immunisation schedule for RV vaccine administration in participating countries. Any regurgitation or vomiting by the subjects after study vaccine administration should be recorded in the eCRF. Concomitant administration of routine pediatric vaccines will be allowed according to local immunisation practices in each participating country.

LAR = Legally Acceptable Representative

The intervals between study visits are presented in [Table 5](#).

**Table 5 Intervals between study visits**

Interval	Optimal length of interval 	Allowed interval
Visit 1→Visit 2	1-2 months	28-83 days † after Dose 1
Visit 2→Visit 3	1-2 months	28-83 days † after Dose 2
Visit 2→Contact ‡	6 months	180-210 days after Dose 2 of HRV vaccine

. Whenever possible the investigator should arrange study visits within this interval.

†. Subjects will not be eligible for inclusion in the Per-Protocol Set (PPS) for immunogenicity if they make the study visit outside this interval.

‡A safety follow-up contact (by telephone call or any other convenient procedure) to collect information on SAEs and medication taken for treatment of the same.

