## **2.2. Secondary objectives**

### **Reactogenicity and safety**

[figure not shown]
- To evaluate the reactogenicity of the liquid HRV vaccine and currently licensed lyophilised HRV vaccine in terms of solicited AEs during the 8 days (Day 0-Day 7) follow-up period after each vaccination.
- To assess the safety of the study vaccines in terms of unsolicited AEs during the 31 days (Day 0-Day 30) follow-up period after each vaccination and Serious Adverse Events (SAEs) during the entire study period.

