**Table 3 Blinding of study epoch**

Study Epoch	Blinding*
Epoch 001	Double-blind
Epoch 001	Observer-blind

\*Double blind for the three lots of PCV-free HRV liquid vaccine and observer-blind for the liquid formulation versus the lyophilised formulation.

- Sampling schedule: Blood samples will be collected from all subjects at Visit 1 and Visit 3 to measure serum anti-RV IgA antibody concentrations using Enzyme Linked Immunosorbent Assay (ELISA).
- Recording of GE episodes: Any GE episodes occurring from Dose 1 of HRV vaccine up to Visit 3 will be recorded for all subjects in the diary card. Parents/Legally Acceptable Representative(s) (LARs) will be instructed to collect stool sample(s) if the subject develops GE during the period from Dose 1 of HRV vaccine up to Visit 3. A stool sample should be collected as soon as possible after illness begins and preferably not later than 7 days after the start of GE symptoms. Two occurrences of diarrhoea will be classified as separate episodes if there will be five or more diarrhoea-free days between the episodes. Refer to the [glossary of terms](#) for definitions of GE and diarrhoea.
- Recording of Solicited AEs: Solicited AEs (fever, fussiness/irritability, loss of appetite, cough/runny nose, diarrhoea and vomiting) occurring between the day of each HRV vaccine dose and the following 7 days (Day 0-Day 7) will be recorded daily using diary cards for all subjects.
- Recording of Unsolicited AEs: Unsolicited AEs occurring within 31 days (Day 0-Day 30) after each dose of HRV vaccine will be recorded using diary cards for all subjects.
- Recording of SAEs: SAEs will be recorded from Visit 1 (Day 0) up to 6 months after Dose 2 of HRV vaccine.
- Type of study: self-contained
- Data collection: Electronic Case Report Form (eCRF)
- Safety monitoring: An IDMC comprising of clinical experts and a biostatistician, will review the safety data accrued during the study and the details of the review will be described in an IDMC charter. The IDMC review will happen after enrolment of 5%, 10% and 50% of subjects. The IDMC review will happen at the following stages:

Review of all safety data for the first 80 enrolled subjects (5% of total enrolment) as soon as data until 8 days post Dose 2 (Day 0-Day 7) are available for 80 subjects.

- any available data beyond 8 days post Dose 2 will also be reviewed.
- during this IDMC review, enrolment of subjects will continue.

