**5.6.14. Recording of AEs and SAEs**

- Refer to Section 8.3 for procedures for the investigator to record AEs and SAEs. Refer to Section 8.4 for guidelines and how to report SAE reports to GSK Biologicals.
- The subjects' parent(s)/LAR(s) will be instructed to contact the investigator immediately should the subjects manifest any signs or symptoms they perceive as serious.

At each vaccination visit, diary cards will be provided to the subject's parent(s)/LAR(s):

- Recording of GE episodes: Any GE episodes occurring from Dose 1 of HRV vaccine up to Visit 3 will be recorded for all subjects in the diary card. Parent(s)/LAR(s) will be instructed to collect stool sample(s) if the subject develops GE during the period from Dose 1 of HRV vaccine up to Visit 3. A stool sample should be collected as soon as possible after illness begins and preferably not later than 7 days after the start of GE symptoms. Two occurrences of diarrhoea will be classified as separate episodes if there will be five or more diarrhoea-free days between the episodes. Refer to the [glossary of terms](#) for definitions of GE and diarrhoea.
- Recording of Solicited AEs: Solicited AEs (fever, fussiness/irritability, loss of appetite, cough/runny nose, diarrhoea and vomiting) occurring between the day of each HRV vaccine dose and the following 7 days (Day 0-Day 7) will be recorded daily using diary cards for all subjects.
- Recording of Unsolicited AEs: Unsolicited AEs occurring within 31 days (Day 0-Day 30) after each dose of HRV vaccine will be recorded using diary cards for all subjects.
- Recording of SAEs: SAEs will be recorded from Visit 1 (Day 0) up to 6 months after Dose 2 of HRV vaccine.
- Collect and verify completed diary cards during discussion with the subject's parent(s)/LAR(s) on Visit 2 and Visit 3.
- Any unreturned diary cards will be sought from the subject's parent(s)/LAR(s) through telephone call(s) or any other convenient procedure.
- The investigator will transcribe the collected information into the eCRF in English.

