**5.6.15. Phone Contact**

A safety follow-up contact will be done by a telephone call to collect information on SAEs and medication taken for treatment of the same.

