#### 11.1.5. Safety

- For analysis of solicited, unsolicited adverse events (such as serious adverse events or adverse events by primary MedDRA term) and for the analysis of concomitant medications, all vaccinated subjects will be considered. Subjects who did not report the event or the concomitant medication will be considered as subjects without the event or the concomitant medication respectively.
- In case there will be more than 5% of subjects without documented dose for solicited symptoms (i.e., symptom screen not completed), sensitivity analysis will include only vaccinated subjects for doses with documented safety data (i.e., symptom screen completed).

- The following rules will be used for the analysis of solicited symptoms:
  - Subject who didn't document the presence or absence of a solicited symptom after one dose will be considered not having that symptom after that dose in the analysis done on "administrated dose"
  - Subjects who documented the absence of a solicited symptom after one dose will be considered not having that symptom after that dose.
  - Subjects who documented the presence of a solicited symptom and fully or partially recorded daily measurement over the solicited period will be included in the summaries at that dose and classified according to their maximum observed daily recording over the solicited period.
  - Subjects who documented the presence of a solicited symptom after one dose without having recorded any daily measurement will be considered as having that symptom after that dose).

- For the analysis, temperatures will be coded as follows for oral, axillary or tympanic route:

Grade	Temperature
0	< 38.0°C
1	≥ 38.0°C - < 38.5°C
2	> 38.5°C - < 39.5°C
3	> 39.5°C

- Note that for all tables described in this section, the way the percentage of subjects will be derived will depend on the event analysed (see table below for details). As a result, the N value will differ from one table to another.

Event	N used for deriving % per subject for Vaccination phase	N used for deriving % per dose for Vaccination phase
Concomitant vaccination	All subjects with study vaccine administered	All study visits with study vaccine administered

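### Visit 3 may take place, and the diary be returned, up to two full days before the post-Dose 2 window for unsolicited adverse events ends, with no step to collect the remainder

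*Protocol*

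**What the plan says.** Protocol 2.2 sets the secondary safety objective over "unsolicited AEs during the 31 days (Day 0-Day 30) follow-up period after each vaccination". Protocol Section 3 names the tool: "Unsolicited AEs occurring within 31 days (Day 0-Day 30) after each dose of HRV vaccine will be recorded using diary cards".

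Table 5 allows Visit 3 at "28-83 days † after Dose 2", and its footnote makes the same interval the limit for the per-protocol set (PPS). In Table 4, cards are handed out at Visits 1 and 2 and returned at Visits 2 and 3. Section 5.6.14 instructs sites to "Collect and verify completed diary cards during discussion with the subject's parent(s)/LAR(s) on Visit 2 and Visit 3". The Table 4 row for non-serious AEs is marked at Visits 1, 2 and 3 and is blank at the extended contact.

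That contact falls 180-210 days after Dose 2, and Section 5.6.15 limits its purpose: "A safety follow-up contact will be done by a telephone call to collect information on SAEs and medication taken for treatment of the same". Protocol 8.3.1 nevertheless requires every AE starting by Day 30 after each dose to be entered in the eCRF.

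On the analysis side, SAP Amendment 1, Section 11.1.5, states: "Subjects who did not report the event or the concomitant medication will be considered as subjects without the event". Its denominator for unsolicited symptoms is all vaccinated subjects. The only short follow-up deviation in SAP 5.3 is less than 180 days, and the sensitivity analysis on documented doses (SAP 6.4.2 and 11.1.5) concerns solicited symptoms only.

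**The concern.** The visit that takes back the post-Dose 2 diary may come before the period that the diary is meant to cover has ended. A non-serious AE that starts after a day-28 visit and by the end of Day 30 must be recorded, yet no planned contact asks about it in time. The SAP then counts the infant as observed for the whole window and free of that event, so the shortfall shows in no table.

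What is at stake is whether a rate labelled 31-day means that for every infant. The unsolicited AE tables, including the by-country summaries in SAP 6.4.2, would mix windows of slightly different length without saying so.

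**Working it through.** **Length of the window.** Day 0 to Day 30 is 30 − 0 + 1 = 31 days, as the protocol states.

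**Days lost for a Visit 3 on day v after Dose 2.** If the visit day counts as observed, the loss is max(0, 30 − v). If the whole visit day counts as lost, it is max(0, 31 − v). The visit day is partly observed, so the truth lies between the two.

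| Visit 3 on day | Full days lost | Counting the visit day as lost | Share of 31 days |
|---|---|---|---|
| 28 | 2 | 3 | 6.5% to 9.7% |
| 29 | 1 | 2 | 3.2% to 6.5% |
| 30 | 0 | 1 | 0% to 3.2% |
| 31 or later | 0 | 0 | 0% |

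**Against the planned output.** The endpoint in Protocol 10.2 is unsolicited AEs after any dose. Two windows of 31 days make 62 days if they do not overlap, so two full days are 2/62 = 3.2%, and 3/62 = 4.8% if the visit day is counted as lost.

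**Dose 1.** Visit 2 may also fall on day 28, but a new card is issued then. SAP 11.1.2 assigns an event to the most recent dose, so a late Dose 1 event moves to Dose 2 and is not lost. The gap exists only after Dose 2.

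**Effect on a rate.** The documents state no expected AE rate and no expected share of early visits, so both are assumed here. Let p be the 31-day post-Dose 2 rate under constant hazard. With L days lost, the observed rate is 1 − (1 − p)^((31 − L)/31).

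- p = 5%, L = 2: 4.69% observed, a drop of 0.31 points for a day-28 infant.
- p = 40%, L = 2: 37.99% observed, a drop of 2.01 points.
- With L = 3 the drops are 0.47 and 3.04 points.

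Multiply by the share f of infants seen on day 28. With L = 2, f = 5% and p = 5% give 0.05 × 0.31 = 0.02 points; f = 50% and p = 40% give 0.50 × 2.01 = 1.0 point. With L = 3 the most extreme case is 0.50 × 3.04 = 1.5 points.

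The planned per-subject rate is after any dose. If p is the same after each dose, its drop is (1 − p) times the single-dose drop, because an infant with an AE after Dose 1 is already counted. With L = 2, p = 5% gives 0.95 × 0.31 = about 0.3 points, and p = 40% gives 0.60 × 2.01 = 1.2 points, each for a day-28 infant. With f = 50% the latter becomes 0.6 points for the group.

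**Share of early visits.** The only visit-timing figures are the illustrative ones in SAP Template 7, copied from ROTA-061. Outside 30-48 days there were 1 + 4 + 4 + 5 = 14 infants; outside 21-48 days, 1 + 2 + 4 + 3 = 10. The difference, 4 of 287 + 294 + 291 + 289 = 1161 (0.3%), is the number seen on days 21-29. That table's protocol limit was 30 days, so the figure does not forecast a trial whose window opens at day 28.

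**The case against.** The best defence is that the duty to record is explicit. Protocol 8.3.1 requires AEs to Day 30 in the eCRF. Section 5.6.14 speaks of completed cards and has sites chase unreturned ones by telephone or another convenient route. A card still running on day 28 need not count as complete, and the Study Procedures Manual, which is not among these documents, may say how to handle it. So a reader who infers that such an AE has no route into the database goes too far. What stands is narrower: the duty has no scheduled step behind it. Section 8.5.1.1 only follows AEs already documented, and at later contacts; after a day-28 visit none is scheduled before Day 31.

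A second defence is that day 28 is the outer tolerance. Table 5 gives 1-2 months as the optimal interval and asks sites to keep to it where possible. This stands as a reason not to assume that many infants come that early. A reader might suppose 10% to 30% of the 1600, but nothing in the documents supports that or any other share.

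A third is that little depends on the result. Allocation uses minimisation on centre and country (Protocol 5.2.2.2.1), so early visits should be spread evenly over the groups, and SAP Section 7 makes all safety analyses descriptive. This stands in full.

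**Conclusion.** The mismatch is real and minor. Table 5, the return of the diary at Visit 3 and the Day 0-Day 30 window do not fit together for visits before day 31, and the SAP would not reveal how often this happened. A day-28 visit costs at most two full days plus the remainder of the visit day. The consequence is a small understatement of absolute rates of non-serious unsolicited AEs. On the assumed ranges and two days lost, it is about 0.02 to 1.0 points on a post-Dose 2 rate, and less on the planned any-dose rate.

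Three stronger readings are not supported:

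- A loss of three days (9.7%) treats the whole of the visit day as unobserved. On that count visits on day 30 are affected too.
- A bias between vaccine groups would need visit timing to depend on the group, and nothing in the plan suggests that.
- By-country summaries need not be incomparable. Visit timing may differ by country, but the documents give no figures and the effect per infant is small.

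Serious AEs and AEs leading to withdrawal are recorded to the final contact. No co-primary result or power figure changes. The size estimate rests on constant hazard and on assumed AE rates and shares of early visits.

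**What to change.** Reconcile Table 5 with the AE window in three parts.

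1. In Table 5, schedule Visit 3 from day 31 after Dose 2 (31-83 days), and keep 28-83 days as the PPS limit for the blood sample. No infant leaves the PPS, and no vaccine dose is affected because none is given at Visit 3.
2. For any visit that still falls on days 28-30, have the parent continue the diary through Day 30 and retrieve it by the route that Section 5.6.14 already provides for outstanding cards. Without this, changing the window would make the gap rarer but would not close it.
3. In the SAP, report by group and country the number of infants with less than 31 days of unsolicited AE follow-up after Dose 2.

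The cost is a protocol amendment and one SAP line. The earliest scheduled Visit 3 moves by three days, which leaves 53 of the present 56 days. Table 5 would carry two limits instead of one, visits on days 28-30 would become scheduling deviations, and a few diaries would need later retrieval. If the visit window is to stay as it is, parts 2 and 3 alone would close the collection gap and make any remaining shortfall visible.
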